Appendix 4. Hepatic Monitoring Tests for Treatment-Emergent Abnormality

Selected tests may be obtained in the event of a treatment-emergent hepatic abnormality and may be required in follow-up with patients in consultation with Lilly or its designee CRP.

Hepatic Monitoring Tests

Hepatic Haematology^a

Haemoglobin
Haematocrit
RBC
WBC
Neutrophils
Lymphocytes
Monocytes
Eosinophils
Basophils
Platelets

Hepatic Chemistry^a

Total bilirubin
Conjugated bilirubin
Alkaline phosphatase
ALT
AST
GGT
CPK

Haptoglobin^a

Hepatic Coagulation^a

Prothrombin time
Prothrombin time, INR

Hepatic Serologies^{a,b}

Hepatitis A antibody, total
Hepatitis A antibody, IgM
Hepatitis B surface antigen
Hepatitis B surface antibody
Hepatitis B core antibody
Hepatitis C antibody
Hepatitis E antibody, IgG
Hepatitis E antibody, IgM

Anti-nuclear Antibody^a

Alkaline Phosphatase Isoenzymes^a

Anti-smooth Muscle Antibody (or Anti-actin Antibody)^a

Abbreviations: ALT = alanine aminotransferase; AST = aspartate aminotransferase; CPK = creatinine phosphokinase; GGT = gamma-glutamyl transferase; Ig = immunoglobulin; INR = international normalised ratio; RBC = red blood cell; WBC = white blood cell.

^a Assayed by Lilly-designated or local laboratory.

^b Reflex/confirmation dependent on regulatory requirements and/or testing availability.

Appendix 5. Blood Sampling Summary

This table summarises the approximate number of venipunctures and blood volumes for all blood sampling (screening, safety laboratories, and bioanalytical assays) during the study. Fewer venipunctures and blood draws may actually occur, but this will not require a protocol amendment.

Protocol I8B-MC-ITSA Sampling Summary for Part A

Purpose	Blood Volume per Sample (mL)	Number of Blood Samples	Total Volume (mL)
Screening tests ^a	20	1	20
Clinical laboratory tests ^a	9	1	9
Pharmacokinetics – insulin lispro	1	21 samples x 2 periods = 42	42
Blood discard for cannula patency	1	21 samples x 2 periods = 42	42
Blood glucose sampling (run-in)	0.6	17 samples x 2 periods = 34	20.4
Blood glucose sampling (MMTT)	0.6	24 samples x 2 periods = 48	28.8
Immunogenicity	5	3	15
Total			177.2
Total for clinical purposes [rounded up to nearest 10 mL]			180

Abbreviation: MMTT = mixed meal tolerance test.

^a Additional samples may be drawn if needed for safety purposes.

Protocol I8B-MC-ITSA Sampling Summary for Part B

Purpose	Blood Volume per Sample (mL)	Number of Blood Samples	Total Volume (mL)
Screening tests ^a	20	1	20
Clinical laboratory tests ^a	9	1	9
Pharmacokinetics – insulin lispro	1	21 samples x 2 periods	42
Blood discard for cannula patency	1	21 samples x 2 periods	42
Blood glucose sampling (run-in)	0.6	17 samples x 2 periods = 34	20.4
Blood glucose sampling (MMTT)	0.6	24 samples x 2 periods = 48	28.8
Immunogenicity	5	3	15
Total			177.2
Total for clinical purposes [rounded up to nearest 10 mL]			180

Abbreviation: MMTT = mixed meal tolerance test.

^a Additional samples may be drawn if needed for safety purposes.

**Appendix 6. Protocol Amendment I8B-MC-ITSA(d)
Summary
A Study to Evaluate the Pharmacokinetics and
Glucodynamics of LY900014 Compared to Humalog in
Children, Adolescents, and Adults with Type 1 Diabetes
Mellitus**

Overview

Protocol I8B-MC-ITSA(c), A Study to Evaluate the Pharmacokinetics and Glucodynamics of LY900014 Compared to Humalog in Children, Adolescents, and Adults with Type 1 Diabetes Mellitus, has been amended. The new protocol is indicated by Amendment (d) and will be used to conduct the study in place of any preceding version of the protocol.

The overall changes and rationale for the changes made to this protocol are as follows:

- Since CCI [REDACTED] is being provided as an option for the MMTT, clarification was added to allow for only this chocolate drink during the MMTT.

Revised Protocol Sections


Note: All deletions have been identified by strikethroughs. All additions have been identified by the use of underline.

**Confidential Information**

The information contained in this document is confidential and the information contained within it may not be reproduced or otherwise disseminated without the approval of Eli Lilly and Company or its subsidiaries.

**Note to Regulatory Authorities:** this document may contain protected personal data and/or commercially confidential information exempt from public disclosure. Eli Lilly and Company requests consultation regarding release/redaction prior to any public release. In the United States, this document is subject to Freedom of Information Act (FOIA) Exemption 4 and may not be reproduced or otherwise disseminated without the written approval of Eli Lilly and Company or its subsidiaries.

LY900014

Study I8B-MC-ITSA is a randomised, patient- and investigator-blind, 2-part study, with each part containing a 2-period crossover assessment in children (age 6 to <12 years), adolescents (age 12 to <18 years), and adults (age 18 to <65 years) with type 1 diabetes mellitus to evaluate the Pharmacokinetics and Glucodynamics of LY900014 compared to Humalog given as a bolus either as a subcutaneous injection or via a continuous subcutaneous insulin infusion pump.

Eli Lilly and Company  
Indianapolis, Indiana USA 46285  
Protocol I8B-MC-ITSA  
Phase 1

Statistical Analysis Plan Version 1 electronically signed and approved by Lilly:  
06 February 2018  
Statistical Analysis Plan Version 2 electronically signed and approved by Lilly on date  
provided below.

Approval Date: 06-Aug-2018 GMT

### 3. Revision History

Statistical analysis Plan (SAP) Version 1 was approved prior to the first patient visit. This version is based on Protocol I8B-MC-ITSA approved on 12 October 2017 and amended on 21 December 2017. This SAP describes the planned analysis of the safety, tolerability, pharmacokinetic (PK), and glucodynamic (GD) data from this study.

This SAP is the second version approved prior to the completion of Part A of the I8B-MC-ITSA Study. The main changes are listed below:

- Clarifying that post-intervention blood glucose samples should not be included in any analysis to determine the PK/pharmacodynamic (PD) profile
- Adding that the observed values equal to 0 for PK parameters will be treated as missing.

## 4. Study Objectives

### 4.1. Primary Objective

The primary objectives of this study are as follows:

- Part A: To evaluate the PK of insulin lispro following a single subcutaneous (SC) bolus dose administered by injection of LY900014 compared to Humalog in children, adolescents, and adults with type 1 diabetes mellitus (T1DM)
- Part B: To evaluate the PK of insulin lispro following a single SC bolus dose administered by continuous subcutaneous insulin infusion (CSII) of LY900014 compared to Humalog in children, adolescents, and adults with T1DM

### 4.2. Secondary Objectives

The secondary objectives of this study are as follows:

- Part A: To evaluate the difference in GD response to LY900014 and Humalog administered by SC bolus injection as assessed using the liquid mixed meal tolerance test (MMTT), in children, adolescents, and adults with T1DM
- Part B: To evaluate the difference in GD response to LY900014 and Humalog administered by SC bolus via CSII as assessed using the liquid MMTT, in children, adolescents, and adults with T1DM
- Part A: To evaluate the tolerability of LY900014 following SC injection in children, adolescents, and adults with T1DM
- Part B: To evaluate the tolerability of LY900014 following SC bolus via CSII in children, adolescents, and adults with T1DM

## 5. Study Design

### 5.1. Summary of Study Design

This is a Phase 1, randomised, 2-part, patient- and investigator-blind, 2-period crossover study in children (age 6 to <12 years), adolescents (age 12 to <18 years), and adults (age 18 to <65 years) with T1DM currently using a CSII pump or multiple daily injection (MDI). The aim is to evaluate insulin lispro PK, GD, safety, and tolerability of LY900014 in comparison with Humalog (reference) following a single dose SC administration immediately prior to a standardised liquid meal.

This study is composed of 2 parts: Part A and Part B. During Part A, patients will receive a single dose of LY900014 and Humalog on 1 occasion each as SC bolus injection and in Part B a single dose of LY900014 and Humalog on 1 occasion each as SC bolus via CSII.

Patients will be randomised on Day 1 of Period 1 in Part A and Day -1 of Period 1 in Part B. For each age group, patients will be randomised to 1 of the 2 treatment sequences (first double-blind LY900014 then double-blind Humalog, and first double-blind Humalog then double-blind LY900014) in 1:1 ratio. In both parts, dosing in Period 1 and Period 2 can occur on consecutive days but not more than 22 days apart. For patients available for dosing on consecutive days, the medical assessments scheduled for Day -1 of Period 2 may be done on Day 1 of Period 1.

Patients will undergo a rescreening visit if dosing visits between Part A and Part B are more than 28 days apart. Patients who participate in Part A may continue to Part B; however, patients who complete Part A but discontinue prior to Part B may be replaced by newly enrolled patients in Part B. Newly enrolled patients will be randomised to 1 of 2 treatment sequences after completing the screening and are expected to complete only Part B activities. Before each MMTT, a run-in period to stabilise blood glucose will occur.

Figure ITSA.5.1 illustrates the design of Part A and Part B.

### 5.2. Determination of Sample Size

The number of patients needed to complete either Part A or Part B of this study was pre-set to 12 in each age group (6 to <12 years, 12 to <18 years, and 18 to <65 years). Twelve completing patients in each age group will provide approximately 90% power to demonstrate 60% increase in the insulin lispro area under the plasma concentration-time curve from time zero to 30 minutes ( $AUC_{[0-30min]}$ ) between LY900014 and Humalog within each age group. The sample size will also provide greater than 85% power to demonstrate 30% reduction in time to early half-maximal drug concentration (early 50%  $t_{max}$ ). The estimated standard deviation of within-subject difference on the log scale is 0.45 for  $AUC_{(0-30min)}$  and 0.35 for early 50%  $t_{max}$ , according to an analysis of internal Lilly data and external published paediatric studies. Testing will be done at an alpha level of 0.05 with a 2-sided confidence interval (CI).

Approximately 45 patients (approximately 15 patients in each age group) may be enrolled in the study to ensure approximately 36 patients complete both inpatient periods (i.e., 12 completers in each age group) for both parts of the study. If patients complete Part A but decline participation

in Part B or drop out from Part A, additional patients may be enrolled to ensure at least 36 patients complete Part B of the study.

## 6. A Priori Statistical Methods

### 6.1. General Considerations

This SAP supersedes the statistical considerations identified in the protocol; where considerations are substantially different, they will be so identified. Data listings, summaries, and analyses will be performed by Covance Early Clinical (EC) Biometrics. If additional analyses are required to supplement the planned analyses described in this SAP, they may be performed and will be identified in the clinical study report (CSR). Any substantial deviations from this SAP will be agreed upon between Eli Lilly and Company and Covance EC Biometrics and identified in the CSR. Any minor deviations from the Tables, Figures, and Listings (TFLs) may not be documented in the CSR.

The analyses for Part A and Part B of the study will be conducted separately using similar statistical methods. Treatment comparisons between LY900014 and Humalog will be conducted at an alpha level of 0.05 with a 2-sided CI within each age group for each part of study.

The age groups used in the PK and GD analyses will be determined by the age of the patient at initial screening. For patients who participated in both parts of the study, the age at screening of Part A will be used in the analyses for both parts. For patients newly enrolled for Part B only, the age at screening of Part B will be used.

The analysis populations are defined for each study part separately. Primary statistical analyses for PK parameters will be conducted on the set of patients who complete both treatment periods with an identical bolus insulin dose for the MMTTs and have measurable insulin lispro concentrations within each part of the study. Supportive analyses may be done on the key parameters for the patients who complete at least 1 treatment period and have measurable insulin lispro concentrations within each part of the study.

Primary statistical analyses for GD parameters will be conducted on the set of patients who complete both treatment periods with an identical bolus insulin dose for the MMTTs within each part of the study. Supportive analyses may be done on the key parameters for the patients who complete at least 1 treatment period for the MMTT within each part of the study.

The post-intervention glucose samples will be collected in the database; however, the post-intervention glucose data will be excluded from PK and GD analyses.

Safety analyses will be conducted for the set of patients receiving at least 1 dose of the study drug, whether or not they completed all protocol requirements.

All protocol deviations that occur during the study will be considered for their severity/impact and will be taken into consideration when patients are assigned to analysis populations.

Summary statistics (including number of patients, mean, standard deviation or standard error, minimum, and maximum) will be presented for continuous variables. Data from all 3 age groups will be pooled and analysed by a linear mixed-effect model for continuous variables unless otherwise stated in the succeeding subsections. The model will include treatment, sequence, period, age group, and the interaction of treatment and age group as fixed effects and patient

within sequence as a random effect. The primary comparison between LY900014 and Humalog for each age group will be based on the treatment difference or ratio of the given age group from the model.

For categorical data, frequency count and percentages will be presented in the summary table.

Data listings will be provided for all patients up to the point of withdrawal, with any patients excluded from the relevant population highlighted, using all data that are databased. Summary statistics and statistical analyses will generally only be performed for patients included in the relevant analysis population. For the calculation of summary statistics and statistical analysis, unrounded data will be used.

For weight and other clinical lab tests (based on data availability), mean change from baseline is the mean of all individual patients' change from baseline values. Each individual change from baseline will be calculated by subtracting the individual patient's baseline value from the value at the time point. The individual patient's change from baseline values will be used to calculate the mean change from baseline using CCI [REDACTED]

Additional exploratory analyses of the data will be conducted as deemed appropriate.

Data analysis will be performed using CCI [REDACTED] or greater.

Table ITSA.6.1 is a list of the study treatment and age group names that will be used in the statistical TFLs.

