5.5. Justification for Dose

The bolus dose of insulin lispro (LY900014 or Humalog) will be fixed dose by body weight (0.2 U/kg). Based on previous studies of both insulin lispro (Humalog) and LY900014, a 0.2 U/kg prandial dose is necessary to provide measurable PK and GD profiles for both study insulins. This dose level has been previously examined in paediatric patients with another rapid-acting analogue with no apparent hypoglycaemic risk (Fath et al. 2017). Furthermore, the occurrence of hypoglycaemia in patients with T1DM or T2DM participating in previous test meal studies with LY900014 was also low, since patients do not receive significant basal insulin coverage during the course of the MMTT.

Meal size differs between adults and children. Due to this, the volume of the liquid test meal for the MMTT will be adjusted by weight for the child and adolescent patients within the study. However, the adult patients in the study will receive a set volume for the MMTT.

For each patient, the individualised prandial insulin lispro dose in LY900014 and Humalog for each test meal must be kept identical throughout the crossover periods for both Part A and Part B. If the investigator determines that it would be unsafe to repeat the same dose, the patient should be discontinued. A minimum weight of 25 kg is required for this study in order to have sufficient dose **CCI** to characterise both the serum insulin lispro absorption and elimination following study drug administration.

6. Study Population

Eligibility of patients for the study will be based on the results of screening medical history, physical examination, vital signs, clinical laboratory tests, and electrocardiogram (ECG).

The nature of any conditions present at the time of the physical examination and any preexisting conditions will be documented.

Screening may occur up to 28 days prior to Day -1 of Period 1 for both Part A and Part B. Patients who are not enrolled within 28 days of screening may be subjected to an additional medical assessment and/or clinical measurements to confirm their eligibility.

Prospective approval of protocol deviations to recruitment and enrolment criteria, also known as protocol waivers or exemptions, is not permitted.

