6.3.1. Meals and Dietary Restrictions

Patients will be provided standardised liquid meals for the MMTTs, as outlined in the Schedule of Activities (Section 2). An evening meal on the day prior to the MMTT and a meal following completion of the MMTT will also be provided. Patients will be fasted (except for water) for at least 10 hours before each test meal and consume each meal within approximately 15 minutes.

The standardised liquid test meal will use CCI [REDACTED]. For children and adolescents in the study, the volume of the liquid test meal [REDACTED] will be based on the patient's body weight

(kg) during the study (Period 1 of Part A or Period 1 of Part B if patients did not participate in Part A of the study) as described in Table ITSA.2. For adults, the liquid test meal will consist of

CCI [REDACTED] approximately 100 g of carbohydrates total in test meal).

[REDACTED] will be consistent with regard to calorie and nutrient content across all MMTT assessments in the study. For both parts of the study, the patient will not be allowed to consume water for 2 hours after dosing apart from fluid provided with the meal; however, water may be consumed freely afterwards.

Table ITSA.2. Volume of Standardised Meal According to Body Weight

Body Weight (kg)	Volume of Meal (mL)
25-29	230
30-34	272
35-39	315
40-44	357
45-49	400
50-54	442
>55	474 CCI [REDACTED]

While resident in the study site, patients may not consume any food or caloric drinks other than that provided by the study site. When not resident in the study site, patients may resume their regular diet.

Following completion of study procedures, patient will be offered a meal. The study site will record dose and time of prandial insulin administered with end-of-study meal.

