7.2.1. Selection and Timing of Doses

The SC injection dose and bolus dose via CSII of insulin (LY900014 and Humalog) will be 0.2 U/kg body weight to cover the carbohydrate content of the standardised liquid test meal. The insulin dose will be determined from the body weight in Period 1 of Part A or Period 1 of Part B if patients did not participate in Part A of the study. This insulin dose (U) of LY900014 and Humalog for each patient must be used for the test meals throughout the crossover periods in Part A and Part B. The same total dose will be administered to a particular patient in both parts of the study and if the investigator determines it would be inappropriate to administer this dose, the patient will be discontinued from the study.

The doses will be administered at approximately the same times on Day 1 of each period. The actual time of all dose administrations will be recorded in the patient's electronic case report form (eCRF).

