10.3. Statistical Analyses

Statistical analysis of this study will be the responsibility of Eli Lilly and Company or its designee.

The analyses for Part A and Part B will be conducted separately using similar statistical methods. Primary statistical analyses will be conducted on the set of patients who complete both treatment periods. Supportive analyses may be done on the key parameters for the patients who complete at least one treatment period. Safety analyses will be conducted for the set of patients receiving at least 1 dose of the study drug, whether or not they completed all protocol requirements.

Summary statistics (including number of patients, mean, standard deviation or standard error, minimum, and maximum) will be presented for continuous variables. Data from all 3 age groups will be pooled and analysed using a linear mixed-effect model for continuous variables unless otherwise stated in the succeeding subsections. The model will include treatment, sequence, period, age group, and the interaction of treatment and age group as fixed effects and patient within sequence as a random effect. The primary comparison between LY900014 and insulin

lispro for each age group will be based on the treatment difference or ratio of the given age group from the model.

Unless otherwise noted, all tests of treatment effects will be conducted at a 2-sided alpha level of 0.05, and CIs will be calculated at 95%, 2-sided.

Any change in the data analysis methods described in the protocol will require an amendment only if it changes a principal feature of the protocol. Any other change to the data analysis methods described in the protocol and the justification for making the change will be described in the study results.

Additional exploratory analyses of the data will be conducted as deemed appropriate.

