10.3.3.2. Glucodynamic Statistical Inference

Summary statistics (including number of patients, mean, standard deviation or standard error, minimum, and maximum) will be presented by treatment for each age group. The GD parameters on the original scale (not log transformed) will be analysed using the same model used for PK parameters. Least-squares means, treatment differences in LSmeans, and the corresponding 95% CIs for the treatment differences will be estimated from the model. The treatment ratios and 95% CIs for the ratios will be calculated using the Fieller's theorem.

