### **6.4.2. Glucodynamic Statistical Inference**

The population for GD statistical analyses is defined in Section 6.1. The GD parameters will be summarized by treatment and age group for each part of the study.

The GD parameters on the original scale (not log transformed) will be analysed using the same model used for PK parameters. Least-squares means, treatment differences in LSmeans, and the corresponding 95% CIs for the treatment differences will be estimated from the model. The treatment ratios and 95% CIs for the ratios will be calculated using Fieller's theorem.

The above analyses may be repeated for the patients who complete at least 1 treatment period for the MMTT.

An exploratory analysis on the interaction between treatment and age group will be evaluated for all GD parameters using the same statistical model used for treatment comparison. This test will be used to compare whether the LY900014 versus Humalog treatment effect is similar among all 3 age groups. The interaction effects will be evaluated using a significance level of 0.10.

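### Does leaving the glucodynamic comparison as a difference or a ratio leave the result open to choice?

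*SAP*

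**What the plan says.** SAP section 6.1 gives one general sentence for continuous variables: "The primary comparison between LY900014 and Humalog for each age group will be based on the treatment difference or ratio". Protocol section 10.3 has the same rule, "for each age group will be based on the treatment difference or ratio of the given age group from the model". Neither sentence mentions GD parameters.

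The later sections fill this in by type of parameter:

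- **Log-transformed Cmax and AUC (SAP 6.3.2).** Only a ratio of geometric means is planned.
- **GD parameters (SAP 6.4.2; protocol 10.3.3.2).** The analysis is on the original scale. LSmean differences with 95% CIs are estimated from the model. In a separate sentence, "The treatment ratios and 95% CIs for the ratios will be calculated using Fieller's theorem". The two are not ranked. PK time parameters are handled in the same way.
- **Similarity across age groups (SAP 6.4.2).** An exploratory treatment-by-age-group test at 0.10 uses the same untransformed model: "This test will be used to compare whether the LY900014 versus Humalog treatment effect is similar among all 3 age groups".

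The secondary GD objectives in SAP section 4.2 are to evaluate a difference in response between the two insulins.

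**The concern.** ΔAUC(0-2h) and ΔAUC(0-5h) are the named secondary GD endpoints. Each has the pre-meal baseline subtracted, so a Humalog mean could in principle be near zero or negative, where a ratio is unstable or reverses its direction. No rule covers that case.

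The design also gives a reason to expect Humalog means that differ by age group. The bolus "will be 0.2 U/kg body weight to cover the carbohydrate content of the standardised liquid test meal" in every patient, and the meal is scaled to weight for children and adolescents. "However, the adult patients in the study will receive a set volume for the MMTT", which is "approximately 100 g of carbohydrates total in test meal". If the Humalog means differ and there is a treatment effect, the difference and the ratio cannot both be constant over age groups.

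Part A is meant to inform the paediatric Phase 3 design. A sponsor free to pick the measure after seeing the data could pick the more convenient age pattern.

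**Working it through.** **The plan's own figures.** No GD mean, SD or power is stated, so there is no GD figure to reproduce. The sample-size section covers two PK endpoints, checked here with a paired t-test, n = 12, 11 df, two-sided 0.05:

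- AUC(0-30min): ln(1.6) = 0.470, SD 0.45, noncentrality 0.470/(0.45/√12) = 3.62, power 90.8% (plan: about 90%).
- Early 50% tmax: |ln(0.7)| = 0.357, SD 0.35, noncentrality 3.53, power 89.4% (plan: above 85%).

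Neither depends on this point.

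**Do the two measures disagree on significance?** Let T and H be the LY900014 and Humalog LSmeans in one age group, with variances v_T and v_H and covariance c. The Fieller set is every θ with (T − θH)² ≤ t²(v_T − 2θc + θ²v_H). At θ = 1 this reads (T − H)² ≤ t²·Var(T − H), which is the condition for the difference CI to contain 0. With common degrees of freedom the verdicts are therefore identical. A check on 20,000 random pairs found 0 mismatches.

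**When does Fieller fail?** The set is bounded only if H² > t²v_H, that is, when the CI for the Humalog mean excludes zero. With 36 within-patient differences and 4 fitted parameters, df = 32 and t = 2.037. At n = 12 the limit is |H|/SD > 2.037/√12 = 0.588. The planned method thus shows a weak denominator by itself.

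**How far can the ratio move for one difference?** Assumed inputs: equal SDs, within-patient correlation 0.5, observed difference −0.75 SD. The difference CI has half-width 2.037 × √(2 × 0.5/12) = 0.588, giving −1.34 to −0.16.

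| Humalog mean/SD | Ratio | Fieller 95% CI |
|---|---|---|
| 3 | 0.75 | 0.58 to 0.94 |
| 2 | 0.63 | 0.37 to 0.91 |
| 1 | 0.25 | −0.55 to 0.79 |
| −1 | 1.75 | 1.12 to 3.70 |

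Every interval excludes 1, in line with the difference CI excluding 0. The last row shows the sign problem: a reduction appears as a ratio above 1.

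**Does the design imply a particular age pattern?** Adults at 100 g and 0.2 U/kg receive 100/(0.2 × weight): 10.0, 7.1 and 5.6 g per unit at assumed weights of 50, 70 and 90 kg. Table ITSA.2 gives 39.7 to 46.0 mL per unit from 25 to 59 kg, but the volume is capped at 474 mL above 55 kg: 474/(0.2 × 65) = 36.5, and 33.9 and 29.6 at 70 and 80 kg. Heavier adolescents therefore move the same way as adults. The adult load is readable only in grams and the paediatric load only in mL, so the two cannot be put on one scale.

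**How sensitive is the age pattern?** Simulated trials, 12 per group, SD 1, correlation 0.5. The middle column takes a true difference of −0.75 in every group; the right-hand column takes a common ratio of 0.625.

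| Humalog means (children, adolescents, adults) | Adults have lowest ratio | Interaction test rejects at 0.10 |
|---|---|---|
| 3, 3, 2 | about 70% | 22% |
| 3, 3, 2.5 | about 51% | 13% |
| 3, 3, 2.75 | about 41% | 11% |

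Chance alone would give one third and 10%. With means 3, 2.5, 2.5, adolescents and adults each have the lowest ratio in about 41%. The result follows the assumed means, which neither document supplies.

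**The case for a change.** The strongest case for acting is that the text does not rank the two GD measures. The general rule in 6.1 yields to later sections, but 6.4.2 lists both again. The ratio can misstate direction when the Humalog mean is negative. The GD results have real use after Part A, and the remedy would be a few sentences with no new data.

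Three parts of this stand: the ranking is unwritten, a signed denominator is a poor basis for a ratio, and two scales can show different age patterns. None of them changes what the plan produces. Both measures must be reported, so neither can be dropped to suit the data without departing from the SAP. No ranking or comparison of ratios between age groups is planned.

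A near-zero or negative Humalog mean is possible but not indicated. Adults take about 100 g of carbohydrate, and protocol section 5.5 says that patients have little basal cover during the test and that hypoglycaemia in earlier test-meal studies of LY900014 was low. If the mean were weak, the Fieller set would be unbounded. If it were clearly negative, the reported LSmeans and difference would show the direction.

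**Conclusion.** This is a gap in labelling that analysts will fill sensibly: the ratio for log-transformed parameters and the LSmean difference for untransformed GD parameters. The wording of the objectives, the separate sentence for the Fieller ratio and the scale of the interaction test all point that way, although none states it outright.

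The effect on within-group significance is nil, given the same model and common degrees of freedom. The effect on effect-size reporting is limited to the ratio column, which stands beside the difference and its CI. The divergence across age groups cannot be quantified from the documents, and the simulated percentages are not a measure of it. GD is a secondary objective in a Phase 1 study, and the interaction test is exploratory. Naming the difference in the SAP would change no analysis, table or decision, so no change is called for.
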